3.7.5.2 Chimerism studies will be obtained at time of relapse

3.7.5.3 Record of all medication administered during inpatient course

3.8 Post transplant re-staging of disease

3.8.1 Bone marrow aspirate and biopsy with cytogenetic evaluations will be obtained:

3.8.1.1 Day 84 (± 7 days), at one year (± 30 days), and whenever there is evidence of relapse

3.9 Study Medications

All medications used in this study are commercially available

3.9.1 Fludarabine:

Fludarabine is a fluorinated nucleotide analogue of the antiviral vidarabine. It acts as a purine antagonist antimetabolite. Synonyms: 2-F-ara-AMP. Bone-marrow suppression from fludarabine is dose-limiting, manifesting as neutropenia, thrombocytopenia, and anemia. Other adverse effects include fever, chills, cough, Dyspnea, pneumonia, gastrointestinal disturbances, stomatitis, edema, the tumor lysis syndrome, skin rashes, auto-immune hemolytic anemia and thrombocytopenia, and hemorrhagic cystitis. Neurological disturbances include peripheral neuropathy, agitation, confusion, visual disturbances, seizures, and coma; high doses have been associated with progressive encephalopathy, blindness, and death. Dosage should be reduced in renal impairment and fludarabine should not be given if creatinine clearance is less than 30 mL/minute. Intravenous fludarabine phosphate is rapidly dephosphorylated to fludarabine, which is taken up by lymphocytes and rephosphorylated to the active triphosphate nucleotide. Peak intracellular concentrations of fludarabine triphosphate are seen about 4 hours after a dose. Fludarabine has a bioavailability of about 50 to 65% after doses of the phosphate by mouth. Clearance of fludarabine from the plasma is triphasic with a terminal half-life of about 20 hours. Elimination is mostly via renal excretion: 60% of a dose is excreted in the urine. The pharmacokinetics of fludarabine exhibit considerable interindividual variation.

3.9.2 Busulfan:

The major adverse effect of busulfan with standard doses is bone-marrow suppression, manifest as leucopenia, thrombocytopenia, and sometimes, anemia. The nadir of the granulocyte count usually occurs after about 10 to 30 days with recovery occurring over up to 5 months, but busulfan has sometimes caused irreversible or extremely-prolonged bone-marrow depression. Hyperpigmentation is common, and in a few cases after long-term therapy may be part of a syndrome simulating Addison's disease. Rarely, progressive interstitial pulmonary fibrosis, known as 'busulfan lung', can occur on prolonged treatment. Gastrointestinal disturbances are rare at usual therapeutic doses but may be dose-limiting where high doses are given before bone marrow transplantation. Other rare adverse effects include dry skin and other skin reactions, liver damage, gynaecomastia, cataract formation, and, at high doses, CNS effects including convulsions. Busulfan may result in impaired fertility and gonadal function. As with other alkylating agents, it is potentially carcinogenic, mutagenic, and teratogenic.

Busulfan is readily absorbed from the gastrointestinal tract and rapidly disappears from the blood with a half-life of 2 to 3 hours. It is extensively metabolized and excreted in the urine almost entirely as sulfur-containing metabolites. It crosses the blood-brain barrier.

Busulfan is an antineoplastic with a cell-cycle non-specific alkylating action unlike that of the nitrogen mustards, and having a selective depressant action on bone marrow. In small doses, it depresses granulocytopoiesis and to a lesser extent

thrombocytopoiesis but has little effect on lymphocytes. With larger doses, severe bone-marrow depression eventually ensues.

3.9.3 Rabbit antithymocyte globulin:

Antithymocyte globulins are antibodies, which act against lymphocytes, and in particular against T-cells, to produce suppression of cell-mediated immunity. Common adverse reactions include fever, chills, and skin reactions including rash, pruritus, and urticaria, which may be manifestations of hypersensitivity. Dyspnea, hypotension, chest, back or flank pain may indicate anaphylaxis, which can occur in up to 1% of patients. Rashes and arthralgia may represent serum sickness, especially in patients with aplastic anemia. Use with other immunosuppressants may reduce the incidence or severity of hypersensitivity but increase the risk of acquired systemic infections, such as CMV or herpes simplex. Enhanced immunosuppression may also increase the incidence of post-transplant lymphoproliferative disease or other malignancies. Leucopenia and thrombocytopenia are also common. Although usually transient, dosage adjustment may be necessary if they become severe or prolonged, and if unrelenting, they may warrant stopping therapy. Other adverse effects include headache, abdominal pain, gastrointestinal disturbances, hypertension, peripheral edema, asthenia, hyperkalaemia, and tachycardia. Nephrotoxicity has been reported.

3.10 Outline of Treatment Plan

Eligible patients who have signed informed consent will undergo pre-transplant evaluation and clearance as per current transplant program standard operating procedures. Patients will be admitted to Hackensack University Medical Center for the administration of the fludarabine, busulfan, TBI and for the transplant procedures

Table 1: Treatment Schema for Conditioning Regimen

	Day of Transplant											
	-6	-5	-4	-3	-2	-1	0	+1	+3	+6	+9	+11
Fludarabine 40mg/m²	X	X	X	X								
Busulfan 130 mg.m²	X	X	X	X								
rATG				X	X	X						
TBI 200 cGY (as randomized)							X/ X					
Tacrolimus					X→							
Stem cell infusion							X					
Methotrexate 5 mg/m²							X	X	X		X	
Filgrastim 5 ug/kg										X→		

3.10.1 Conditioning Regimens

Eligible patients who have signed informed consent will be randomized to treatment arm A (Flu-Bu) or treatment arm B (Flu-Bu-TBI).

3.10.2 Treatment arm A:

- 3.10.2.1 Patients must be admitted to HUMC prior to the start of the fludarabine and will not be discharged until engraftment has occurred.
- 3.10.2.2 Fludarabine will be administered at a dose of 40/mg/m² IV daily for 4 days starting on transplant day -6.
- 3.10.2.3 Busulfan will be administered immediately following the fludarabine at a dose of 130 mg/m² IV daily for 4 days starting on transplant day -6.
- 3.10.2.4 Patients will also receive rabbit antithymocyte globulin (Thymoglobulin) at a dose of 0.5 mg/kg IV on day -3, and 1.5 mg/kg on day -2 and 2 mg/kg on day -1
- 3.10.2.5 Hematopoietic cells will be infused on day 0
- 3.10.2.6 Graft versus host disease (GVHD) prophylaxis will consist of tacrolimus 0.03 mg/kg (or 0.015 mg/kg for age \geq 65) using ideal body weight, IV total daily dose starting on transplant day -2 and adjusted based on blood levels. Methotrexate at a dose of 5 mg/m² IV will be administered on transplant days +1, +3, +6 and +11
- 3.10.2.7 Dose adjustment for the fludarabine, busulfan and antithymocyte globulin will be as follows:
 - 3.10.2.7.1 If patient weighs less than 100% of ideal body weight (IBW), dosing is based on actual body weight
 - 3.10.2.7.2 If patient weighs 120-150% of IBW, dosing is based on adjusted body weight (ABW)
 - 3.10.2.7.3 If patient weighs greater than 150% of IBW, actual weight will be capped at 150% of ideal body weight, and this will be used in the adjusted body weight formula
- 3.10.2.8 Corrected body weight formula: ABW= IBW + [(0.25) x (actual BW-IBW)]

3.10.3 Treatment arm B:

- 3.10.3.1 Patients must be admitted to HUMC prior to the start of the fludarabine and will not be discharged until engraftment has occurred.
- 3.10.3.2 Fludarabine will be administered at a dose of 40/mg/m² IV daily for 4 days starting on transplant day -6.
- 3.10.3.3 Busulfan will be administered immediately following the fludarabine at a dose of 130 mg/m² IV daily for 4 days starting on transplant day -6.
- 3.10.3.4 Total body irradiation will be given in 2 fractions of 200 CGY (total 400 CGY) on day -1.

3.10.3.5 All patients in treatment arm B will also receive rabbit antithymocyte globulin (Thymoglobulin) at a dose of 0.5 mg/kg IV on day -3, and 1.5 mg/kg on day -2 and 2 mg/kg on day -1.

3.10.3.6 Hematopoietic cells will be infused on day 0.

3.10.3.7 Graft versus host disease (GVHD) prophylaxis will consist of tacrolimus 0.03 mg/kg (or 0.015 mg/kg for age \geq 65) using ideal body weight, IV total daily dose starting on transplant day -2 and adjusted based on blood levels. Methotrexate at a dose of 5 mg/m² IV will be administered on transplant days +1, +3, +6 and +11.

3.10.3.8 Dose adjustment for the fludarabine, busulfan and antithymocyte globulin will be as follows:

- 3.10.3.8.1 If patient weighs less than 100% of ideal body weight (IBW), dosing is based on actual body weight.
- 3.10.3.8.2 If patient weighs 120-150% of IBW, dosing is based on adjusted body weight (ABW).
- 3.10.3.8.3 If patient weighs greater than 150% of IBW, actual weight will be capped at 150% of ideal body weight, and this will be used in the adjusted body weight formula.

3.10.3.9 Corrected body weight formula: ABW= IBW + [(0.25) x (actual BW-IBW)]

3.10.4 Stem cell infusion:

Day 0 for purposes of methotrexate administration is defined as the day the HSC infusion is completed. The infusion of peripheral blood stem cells will be done in accordance with the Blood and Marrow Transplant program standard operating procedures

3.10.5 Graft versus host disease (GVHD) prophylaxis:

GvHD prophylaxis consists of tacrolimus 0.03 mg/kg (or 0.015 mg/kg for age \geq 65) using ideal body weight, IV total daily dose starting on transplant day -2 and adjusted based on blood levels. Methotrexate at a dose of 5 mg/m² IV will be administered on transplant days +1, +3, +6 and +11

3.10.6 Supportive care after transplantation

Supportive care including transfusions, hydration and prophylactic antibiotics will be provided as per current transplant program standard operating procedures.

3.10.7 Post-transplant cytokine administration

Filgrastim will be administered at a dose of 5 mcg/kg (rounded to vial size) every day starting on day+9 until neutrophil engraftment

3.10.8 GvHD management

Management of GvHD is not defined in this protocol. Patients may be treated in accordance with usual practices and are encouraged to enroll into clinical studies of the management of these complications of transplantation. Supportive care including

transfusions, hydration and prophylactic antibiotics will be provided as per current transplant program standard operating procedures.

4 ADVERSE EVENTS

4.1 Definitions

4.1.1 Adverse Event Definition

An adverse event (AE) is any untoward medical occurrence in a patient administered a pharmaceutical product, which does not necessarily have a causal relationship with the treatment. An adverse event can be any unfavorable and unintended sign (eg, including an abnormal laboratory finding), symptom, or disease temporally associated with the use of the drug, whether or not it is considered to be drug related. This includes any newly occurring event or previous condition that has increased in severity or frequency since the administration of drug.

4.1.2 Serious Adverse Event Definition

A serious adverse event (SAE) is any adverse event, occurring at any dose and regardless of causality that:

- 4.1.2.1 Results in death.
- 4.1.2.2 Is life-threatening. Life-threatening means that the patient was at immediate risk of death from the reaction as it occurred, i.e., it does not include a reaction which hypothetically might have caused death had it occurred in a more severe form.
- 4.1.2.3 Requires inpatient hospitalization or prolongation of existing hospitalization. Hospitalization admissions and/or surgical operations scheduled to occur during the study period, but planned prior to study entry are not considered AEs if the illness or disease existed before the patient was enrolled in the trial, provided that it did not deteriorate in an unexpected manner during the trial (eg, surgery performed earlier than planned).
- 4.1.2.4 Results in persistent or significant disability/incapacity. Disability is defined as a substantial disruption of a persons' ability to conduct normal life functions.
- 4.1.2.5 Is a congenital anomaly/birth defect.
- 4.1.2.6 Is an important medical event. An important medical event is an event that may not result in death, be life-threatening, or require hospitalization but may be considered an SAE when, based upon appropriate medical judgment, it may jeopardize the patient or subject and may require medical or surgical intervention to prevent one of the outcomes listed in the definitions for SAEs. Examples of such medical events include allergic bronchospasm requiring intensive treatment in an emergency room or at home, blood dyscrasias or convulsions that do not result in inpatient hospitalization, or the development of drug dependency or drug abuse.

Clarification should be made between the terms “serious” and “severe” since they ARE NOT synonymous. The term “severe” is often used to describe the intensity (severity) of a

specific event (as in mild, moderate, or severe myocardial infarction); the event itself, however, may be of relatively minor medical significance (such as a severe headache). This is NOT the same as “serious,” which is based on patient/event outcome or action criteria described above and are usually associated with events that pose a threat to a patient’s life or functioning. A severe adverse event does not necessarily need to be considered serious. For example, persistent nausea of several hours duration may be considered severe nausea but not an SAE. On the other hand, a stroke resulting in only a minor degree of disability may be considered mild, but would be defined as an SAE based on the above noted criteria. Seriousness (not severity) serves as a guide for defining regulatory reporting obligations.

4.2 Procedures for AE and SAE Reporting

The Principle Investigator-sponsor must report all serious adverse events (SAE) regardless of relationship with any study drug or expectedness to the IRB as required by the institution.

4.3 Intensity for each adverse event, including any lab abnormality, will be determined by using the NCI CTCAE, version 3.0 (or later version), as a guideline, wherever possible. The criteria are available online at <http://ctep.cancer.gov/reporting/ctc.html>.

4.4 Assessment of Toxicity

4.4.1 Common Terminology Criteria for Adverse Events (CTCAE) will be used for the assessment and grading of all toxicities experienced by patients enrolled into this study (http://ctep.cancer.gov/forms/CTCAE_Index.pdf)

- 4.4.1.1 If the nature of the adverse experience is listed in the CTCAE, the maximum grade and time of maximum grade will be reported.
- 4.4.1.2 If the adverse experience is not listed on the NCI CTG Expanded Toxicity Criteria Appendix D, report the toxicity grade using the following criteria.
 - 4.4.1.2.1 **Grade 1 = Mild:** an adverse experience which is easily tolerated by the patient, causing minimal discomfort and not interfering with everyday activities.
 - 4.4.1.2.2 **Grade 2 = Moderate:** an adverse experience which is sufficiently discomforting to interfere with normal everyday activities.
 - 4.4.1.2.3 **Grade 3 = Severe:** an adverse experience which is incapacitating and prevents normal everyday activities.
 - 4.4.1.2.4 **Grade 4 = Life Threatening:** an adverse experience which places the patient at immediate risk of death.

4.5 Assessment of Causality

4.5.1 Every effort should be made by the investigator to explain each adverse experience and assess its relationship, if any, to study drug treatment. Causality should be assessed using the following categories: Not Related, Unlikely, Suspected (*Reasonable Possibility*), Probable.

- 4.5.1.1 **Not related:** The adverse experience is definitely not related to the test drug.
- 4.5.1.2 **Unlikely:** There are other, more likely causes and the drug is not suspected as a cause.
- 4.5.1.3 **Suspected (reasonable possibility):** A direct cause and effect relationship between the drug and the adverse experience has not been demonstrated but there is a reasonable possibility that the experience was caused by the drug.
- 4.5.1.4 **Probable:** There probably is a direct cause and effect relationship between the adverse experience and the study drug.

4.5.2 The degree of certainty with which an adverse experience is attributed to drug treatment (or alternative causes, e.g. natural history of the underlying diseases, concomitant therapy, etc.) will be determined by how well the experience can be understood in terms of one or more of the following:

- 4.5.2.1 Known pharmacology of the drug
- 4.5.2.2 Reaction of similar nature being previously observed with this drug or class of drug. The experience having often been reported in literature for similar drugs as drug related e.g. skin rashes, blood dyscrasia. The experience being related by time to drug ingestion terminating with drug withdrawal (dechallenge) or reproduced on rechallenge

4.6 Follow-up of Adverse Experiences

- 4.6.1 Patients with Grade 3/4 adverse experiences will be actively followed until the event has subsided (disappeared) or until the condition has stabilized.
- 4.6.2 Adverse events, both serious and non-serious, and deaths that occur during the patient's study participation will be recorded in the source documents. All SAEs should be monitored until they are resolved or are clearly determined to be due to a patient's stable or chronic condition or intercurrent illness(es)

5 STATISTICAL EVALUATION

5.1 Primary Objective

The primary objective of this single institution randomized Phase III trial is to compare the 1-year relapse rate of myeloid malignancy in patients receiving two different conditioning regimens. In this study, subjects will be randomly assigned to one of 2 conditioning regimens: fludarabine and busulfan or fludarabine, busulfan and low-dose total body irradiation. The myeloid malignancies include acute myeloid leukemia (AML), chronic myeloid leukemia (CML) and other myeloproliferative diseases, and myelodysplastic syndromes (MDS).

Primary endpoint will be the 1-year event free survival (EFS) for the two treatment groups, where the event is relapse or progression. Patients are considered a failure with respect to EFS if they experience disease relapse or progression. The time to this event is the time from transplant to relapse or progression. Subjects alive without confirmed disease progression will be censored at the time of last disease evaluation. Patients who die without evidence of disease relapse or progression will be censored at time of death and death will not be treated as failure for analysis of this primary endpoint.

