5.4 Sample Size and Power Calculations

The main objective is to compare the relapse-free surviving proportions at 1 year in myeloid malignancy patients who are randomized to either FluBuTBI or FluBu conditioning regimen.

In examining the time to relapse, we consider an analysis of the proportion surviving without relapse/progression at the 1 year endpoint. A comparison of this event between the two treatment arms will be conducted using log-rank test statistics at the 5% level of significance. Based on this statistic, the calculation of sample size was obtained using PASS 2008. According to the results from previous studies [De Lima et al], the 1-year relapse rate in patients with myeloid malignancies being treated with FluBu is 34%. We posit that when the FluBuTBI regimen is used the relapse rate will be reduced to 13.6%, which is 40% of the relapse risk in the FluBu regimen arm. Then, a one-sided log-rank test will be used to examine evidence for a reduction in disease relapse. For the nominal power of 80%, significance level of 5%, 4 year accrual, 1 year follow-up and 10% drop out rate in both FluBuTBI and FluBu treatment arm, 52 patients (26 per arm) will be required to detect the 20.4 difference (60% reduction in relapse rate). This calculation achieved 80.06%. To adjust for balanced samples within the risk status, the study will enroll a maximum of 54 patients (27 per arm).

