5.7 Primary Endpoint

The primary analysis will include all randomized subjects, classified according to their randomized treatment allocation by the *intent-to-treat* principle. The analysis of relapse or disease progression is planned at one year after accrual is completed. The two regimen arms will be compared utilizing a one-sided log rank test stratified on risk status, and using a level significance level of 0.05.

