5.8.4 Event-Free Survival

The event is death from any cause or relapse/disease progression. The time to this event is the time from randomization to death, relapse or disease progression, loss to follow-up or the end of the study, whichever comes first. Patients alive at the time of last observation are considered censored. The Kaplan-Meier estimate of survival will be estimated separately for each treatment-group and risk status. A one-sided log-rank test stratified on risk status will be conducted at the 5% level of significance, analogous to the analysis of relapse risk described above.

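### Event-free survival has two definitions: the primary endpoint in 5.1 censors deaths and starts at transplant, while 5.8.4 counts deaths and starts at randomization

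*Combined protocol and SAP*

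**What the plan says.** Section 5.1 names the primary endpoint and its event: "Primary endpoint will be the 1-year event free survival (EFS) for the two treatment groups, where the event is relapse or progression". It fixes the origin, "The time to this event is the time from transplant to relapse or progression", and the handling of death: "Patients who die without evidence of disease relapse or progression will be censored at time of death and death will not be treated as failure".

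Section 5.8.4, headed Event-Free Survival, defines something else: "The event is death from any cause or relapse/disease progression", with "The time to this event is the time from randomization to death, relapse or disease progression". This second endpoint is missing from both secondary-endpoint lists (5.2 and 5.8.1).

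Section 5.4 adds a third wording: "The main objective is to compare the relapse-free surviving proportions at 1 year in myeloid malignancy patients". Its inputs, however, are relapse rates: 34% for FluBu and 13.6% for FluBuTBI. Sections 2.1 and 5.6 also speak of relapse rates.

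Section 5.7 sets the analysis population: "The primary analysis will include all randomized subjects". Section 5.3 sets one year of follow-up, counted from transplantation. Overall survival starts at the first dose in 5.2.1 and 5.8.1.2, but at randomization in 5.8.2.

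Section 5.2 names the cumulative incidence function for relapse and treatment-related mortality. No section says that it supplies the 1-year rates of the primary endpoint.

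**The concern.** Event-free survival is normally read as the proportion alive and free of relapse. The quantity in 5.1 is not that, because a patient who dies in remission leaves the risk set and never counts as a failure. A report that follows 5.1 could print a death-censored figure under the name EFS, beside a lower EFS from 5.8.4. The first figure exceeds the proportion alive without relapse in any arm that has non-relapse deaths.

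The origins raise a separate problem. An analysis of all randomized subjects needs a time zero for each of them. A subject randomized but never transplanted has none under 5.1, and has no stated one-year follow-up under 5.3. The two origins for overall survival leave a similar choice open to the analyst.

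**Working it through.** **1. The definitions side by side**

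| Section | Name used | Event | Origin |
|---|---|---|---|
| 5.1 | EFS (primary) | relapse or progression; deaths censored | transplant |
| 5.8.4 | EFS | death, relapse or progression | randomization |
| 5.2.1, 5.8.1.2 | OS | death | first dose |
| 5.8.2 | OS | death | randomization |

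**2. Which event the sample size uses.** In 5.4, 0.40 × 34% = 13.6% and 34 − 13.6 = 20.4 points, as the plan states. No mortality enters these inputs, so they fit the event in 5.1 and not the one in 5.8.4. Correcting the name leaves them unchanged.

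**3. Size of the mislabelling.** The documents give no one-year non-relapse mortality (NRM) by arm. Section 5.10 assumes 10% for FluBu, without a clear one-year horizon. As an illustration, take 10% at one year in both arms, treat the plan's rates as death-censored, and let the two risks act independently.

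- Death-censored figure = 1 − relapse: FluBu 1 − 0.34 = 66.0%; FluBuTBI 1 − 0.136 = 86.4%.
- Alive and relapse-free = (1 − relapse)(1 − NRM): 0.66 × 0.90 = 59.4%; 0.864 × 0.90 = 77.8%.
- Overstatement = (1 − relapse) × NRM: 0.66 × 0.10 = 6.6 points; 0.864 × 0.10 = 8.6 points.
- Difference between arms: 86.4 − 66.0 = 20.4 points death-censored; 77.8 − 59.4 = 18.4 points alive and relapse-free.

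If 34% and 13.6% are instead cumulative incidences, alive and relapse-free is 1 − 0.34 − 0.10 = 56.0% and 1 − 0.136 − 0.10 = 76.4%. Under constant hazards the death-censored figure is (1 − tot)^(relapse/tot), with tot = relapse + NRM. That gives 0.56^(0.34/0.44) = 63.9% and 0.764^(0.136/0.236) = 85.6%. The overstatement is then 7.9 and 9.2 points.

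**4. What changes when the rates are cumulative incidences.** Take the plan's rates as death-censored, with constant hazards l = −ln(1 − relapse) and n = −ln(1 − NRM). Then the cumulative incidence of relapse is l/(l + n) × [1 − exp(−(l + n))].

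| Arm | Assumed NRM | l | n | Cumulative incidence | Below the plan's rate by |
|---|---|---|---|---|---|
| FluBu | 10% | 0.4155 | 0.1054 | 32.4% | 1.6 points |
| FluBu | 12% | 0.4155 | 0.1278 | 32.1% | 1.9 points |
| FluBuTBI | 10% | 0.1462 | 0.1054 | 12.9% | 0.7 points |
| FluBuTBI | 20% | 0.1462 | 0.2231 | 12.2% | 1.4 points |

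If every death preceded any relapse, the shortfall would be relapse × NRM. The largest value over these cases is 0.34 × 0.12 = 4.1 points.

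**The case against.** The strongest reply is that the primary endpoint is not ambiguous. Section 5.1 states event, origin and censoring, and 2.1, 5.4, 5.6 and 5.7 all point to relapse. That stands: the event can be identified, and the log-rank test with deaths censored is a valid test of the cause-specific relapse hazard. A reader might infer from the clash of names that the endpoint is undefined or the test invalid, and the documents do not support this.

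It can also be said that the estimator is already in the plan. Section 5.2 names the cumulative incidence function in a paragraph that also covers baseline summaries, so its scope may not be limited to secondary endpoints. No section prescribes a death-censored EFS figure. This largely stands, and what is missing is one sentence linking that estimator to the primary 1-year rates.

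A reader might further infer that subjects replaced under 5.9.2 leave the analysis, or that relapse follow-up ends 28 days after discontinuation. Section 5.7 keeps every randomized subject in the analysis, and the 28 days in 5.9.1 concern adverse-event collection.

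Finally, 3.1 and 5.3 anchor follow-up to transplant, so an origin at randomization is a choice with consequences. That is fair, but the transplant origin leaves untransplanted subjects with no place in the population that 5.7 defines.

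**Conclusion.** The conflicts are real: two events and two origins under one name, a transplant origin set against an all-randomized analysis, and two origins for overall survival. They should be corrected, but they do not undermine the relapse comparison or the choice of test.

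With NRM assumed at 10% at one year in both arms, a death-censored figure called EFS would overstate the proportion alive without relapse by 6.6 points (FluBu) and 8.6 points (FluBuTBI), or by 7.9 and 9.2 points if the plan's rates are cumulative incidences. The documents give no number of randomized but untransplanted subjects, so that effect cannot be sized.

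Two stronger readings should not be drawn. Setting FluBuTBI mortality at the 20% in 5.10 would make the apparent benefit look about twice the real one, but that figure is a three-month stopping level and not an expected one-year rate. Excess deaths would also show in overall survival, the 5.8.4 endpoint, treatment-related mortality and the stopping rule. Nor does this point bear on the power stated in 5.4: renaming the endpoint leaves the inputs alone, and it neither secures nor refutes that power.

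**What to change.** - Rename the primary endpoint in 5.1 *time to relapse/progression, with death without relapse as a competing event*.
- State that its 1-year rates are estimated by the cumulative incidence function already named in 5.2.
- Keep the stratified one-sided log-rank test and label it a test of the cause-specific relapse hazard.
- In 5.4, refer to relapse rates in place of the relapse-free surviving wording.
- Reserve EFS for 5.8.4 and add it to the secondary lists in 5.2 and 5.8.1.
- Start the primary endpoint and overall survival at randomization throughout, to match 5.7 and 5.8.2, and follow untransplanted subjects for relapse and death.
- Read the 1-year rate at one pre-stated day, the same in both arms, late enough to include the one-year marrow in 3.8.1.1. Its ±30-day window runs to about day 395 after transplant (365 + 30), which is later than one year from randomization.

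The cost is mostly wording, plus a follow-up contact for untransplanted subjects. Compared with death-censored figures, reported relapse rates would be about 0.7 to 1.9 points lower per arm under constant hazards, for assumed NRM of 10% to 12% with FluBu and 10% to 20% with FluBuTBI. The gap could reach about 4 points if all deaths came first. The sample-size inputs stay as they are.
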